8.3. Body Surface Area of AD Involvement

The Body Surface Area (BSA) of AD involvement will be assessed as a percentage for eight different parts of the body, and will be reported individually and as an overall BSA (calculated with the sum of all parts combined), as derived in the CRF. The body parts assessed and their highest possible scores are as follows: head and neck [9%], anterior trunk [18%], back [18%], upper limbs [18%], lower limbs [36%], and genitals [1%].

Overall BSA of AD involvement will be summarized descriptively by visit as continuous variables using LOCF and OC. Absolute change and percent from baseline will also be included in the descriptive analysis.

For the LOCF analysis, the imputation will be performed separately for each body part, and the imputed overall BSA will be obtained with the sum of the imputed body region scores.

All BSA data will be listed.

8.4. Scoring Atopic Dermatitis

Scoring Atopic Dermatitis (SCORAD) is a validated measure commonly used in clinical trials and clinical practice to assess the severity and the extent of AD signs and symptoms. SCORAD takes into account the extent and intensity of six types of basic lesions (erythema/darkening, edema/papule, oozing/crusting, excoriation,lichenification/prurigo and dryness) and symptoms (itching and loss of sleep). SCORAD ranges from 0 to 103 and has 3 components: extent, intensity, and subjective symptoms.

Calculation of SCORAD will be performed as follows: The extent of body surface area affected by atopic dermatitis will be the "extent of area involved component" (denoted with A).

Next, the intensity of all basic types of lesions is assessed. Depending on the intensity, each of these is assigned a score of 0 (absence), 1 (mild), 2 (moderate) or 3 (severe). The sum of these scores will estimate the "intensity component" (denoted with B).

Finally, based on a visual analog scale (recorded in centimeters), the presence of irritability and loss of sleep for the past three nights is evaluated as a value between 0 (no symptoms) and 10 (worst symptoms ever had). The sum of the two values will estimate the "subjective symptoms component" (denoted with C).

The SCORAD total score is then calculated as = A/5 + (7*B)/2 + C.

SCORAD will be summarized descriptively by visit using LOCF and OC. Absolute change and percent changes from baseline will also be included in the summary.

For the LOCF analysis, the imputation will be performed separately for each SCORAD component, and the imputated total score will be obtained with the imputed components.

All SCORAD data will be listed.

8.5. Pruritus Numeric Rating Scale

Subject-reported assessments of pruritus will be collected daily on a diary.

The Pruritus Numeric Rating Scale (NRS) will be used by the subjects to report the intensity of their pruritus (itch) during the last 24 hours. The scale for average itch intensity and maximum itch intensity has values in a range between 0 to 10, with 0 being 'no itch' and 10 being 'worst itch imaginable'.

Average and peak Pruritus NRS scores will be obtained based on the average and maximum daily scores during the 7 days immediately preceding each scheduled visit (rounding is not permitted), and will be denoted as "weekly" scores (average weekly and peak weekly, respectively). A minimum of 4 daily scores is required for these calculations, and if less than 4 daily scores are available the respective weekly score will be a missing value.

Weekly average of peak pruritus NRS and weekly average of average pruritus NRS scores will be summarized descriptively by visit as continuous variables using LOCF and OC. Absolute and percent changes from baseline will also be included in the analysis.

Absolute and percent change from baseline in weekly average of peak pruritus NRS and weekly average of average pruritus NRS using LOCF will be displayed graphically.

For the LOCF analysis, the imputation will be performed separately for each weekly average or peak pruritus NRS score.

All pruritus NRS data will be listed.

8.6. Sleep Disturbance Numeric Rating Scale

Subject-reported assessments of sleep disturbance NRS will be collected daily on a diary.

Sleep disturbance NRS is a scale to be used by the subjects to report the degree of their sleep loss related to AD. The scale has values in a range between 0 to 10, with 0 being 'no sleep loss related to signs/symptoms of AD' and 10 being 'I cannot sleep at all due to the signs/symptoms of AD'.

Weekly sleep disturbance NRS scores will be obtained based on the average daily values during the 7 days immediately preceding each scheduled visit. A minimum of 4 daily scores is required for this calculation, and if less than 4 daily scores are available the respective weekly score will be a missing value.

Weekly average sleep disturbance NRS will be summarized descriptively by visit as continuous variables using LOCF and OC. Absolute and percent changes from baseline will also be included in the analysis.

Absolute and percent change from baseline in weekly average sleep disturbance NRS using LOCF will be displayed graphically.

For the LOCF analysis, the imputation will be performed for each weekly average sleep disturbance NRS score.

All sleep disturbance NRS data will be listed.

8.7. Application of Topical Medication for AD

Patient-reported assessments of the use of topical AD medication for their eczema will be collected daily on a diary. Subjects will be instructed to use the authorized background TCS, and will be asked to record the response (yes/no) to the following question, "Did you apply the eczema medication your doctor gave you, to your skin today?", on an electronic device (ie, diary), throughout the clinical trial (including the runin and the follow-up period).

A topical AD medication free day is a day without use of topical AD medication. For each subject, each day will be classified as free or not. Days of topical AD medication use will be calculated by summing up the days recorded as yes on a diary. The daily values in visit interval will be used for calculation of visit informations.

Topical AD medication-free days in each visit interval (see section 6.6) will be calculated as follows:

Topical AD medication-free days in visit interval = Days in the interval – Days of topical AD medication use in the interval.

The number of topical AD free days will be summarized descriptively by visit interval as continuous variables. No imputation will be used.

All data for topical AD medication use will be listed.

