## 8.1.7 Application of Topical Medication for AD: Diary

Subjects will be instructed to use the authorized background TCS as prescribed by the investigator. Each evening, subjects will be asked to record the response (yes/no) to the following question, "Did you apply the eczema medication your doctor gave you, to your skin today?", on an electronic device (ie, diary), throughout the clinical trial (including the run-in and the follow-up period).

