6.6. Analysis Visit Window

Efficacy by-visit summaries will use the analysis visit. Unscheduled and early termination visits will be windowed based on the following analysis visit window. If multiple measurements are taken within the same window, the one taken closest to the target study day will be used for the analysis. If there are multiple measurements with same difference from target day, the later assessment should be used for the analysis.

		Visit	Window
Analysis Visit	Target Study Day	EASI, IGA, BSA, SCORAD	DLQI/cDLQI
Baseline	1	<=1	<=1
Week 1-2	10	2 to 19	NA
Week 4	29	20 to 42	NA
Week 8	57	43 to 71	NA
Week 12	85	72 to 99	NA
Week 16	113	100 to 141	100 to 141
Week 24 Follow-up	169	> 141	> 141

Daily diary efficacy data (pruritus and sleep disturbance NRS) will be classified into analysis visits as follows considering the data during the 7 days immediately preceding each scheduled visit.

This document is confidential.

SAP Version: Final Version 3.0, 21-Sep-2020

Controlled Document ID: 3903A.01, Effective Date 29-Oct-2018

Filing requirements: TMF

Sponsor: Galderma Research & Development, LLC; Protocol No.: RD.06.SPR.116912, Version 6.0

Analysis Visit	Target Study Day	Diary Data Window
Baseline	1	-7 to -1
Week 1-2	10	3 to 9
Week 4	29	22 to 28
Week 8	57	50 to 56
Week 12	85	78 to 84
Week 16	113	106 to 112
Week 24 Follow-up	169	162 to 168

Daily topical AD medication used data will be classified into visit intervals as follows.

Analysis Visit Interval	Target Study Day	Diary Data Window
Baseline to Week 1-2	10	1 to 9
Week 1-2 to Week 4	29	10 to 28
Week 4 to Week 8	57	29 to 56
Week 8 to Week 12	85	57 to 84
Week 12 to Week 16	113	85 to 112
Week 16 to Week 24 follow-up	169	113 to 168

Safety and pharmacokinetics data will not be windowed for by-visit summary. i.e., scheduled visit data will be used for analysis.

7. Demographic, Other Baseline Characteristics and Medication

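### SAP 8.7 counts a diary day with no entry as a topical-medication-free day, so this secondary endpoint can only err upward

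*SAP*

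**What the plan says.** Protocol 6.4.3 lists the number of topical AD medication-free days among the secondary efficacy endpoints. Protocol 8.1.7 describes the source: "Each evening, subjects will be asked to record the response (yes/no) to the following question", namely whether the prescribed eczema medication was applied that day.

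SAP 8.7 turns the diary into the endpoint in three steps:

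- It allows two states for a day: "For each subject, each day will be classified as free or not".
- It defines use: "Days of topical AD medication use will be calculated by summing up the days recorded as yes on a diary".
- It derives the endpoint by subtraction. The formula begins "Topical AD medication-free days in visit interval = Days in the interval" and then takes away the days of use in that interval.

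The same section adds "No imputation will be used". The intervals come from SAP 6.6 ("Daily topical AD medication used data will be classified into visit intervals as follows"), which sets them as fixed ranges of study days.

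The other two diary endpoints have a rule for missing entries. For pruritus, SAP 8.5 says "if less than 4 daily scores are available the respective weekly score will be a missing value". For sleep disturbance, SAP 8.6 says "A minimum of 4 daily scores is required for this calculation". SAP 8.7 has no counterpart.

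**The concern.** An electronic diary day can end in one of three ways: 'yes', 'no' or nothing entered. The SAP formula uses only the 'yes' days, so a day left blank is handled exactly like a day on which the subject reported no use. In effect this is single imputation of non-use, in a section that says nothing will be imputed. The recorded 'no', which would separate the two cases, is collected but not used.

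Blank days cannot be presumed free of use. Under Protocol 7.5.8.1.1, background TCS goes on all lesions as the investigator directs, and Appendix 2 rules out as-needed use. Many blank days, especially before any tapering, may therefore be days of use.

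What is at stake is how the endpoint is read. More medication-free days would be taken as a sign of benefit. Under this rule, poorer diary keeping produces the same sign.

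**Working it through.** **Inputs from the documents.** The SAP 6.6 windows for this diary are Days 1–9, 10–28, 29–56, 57–84, 85–112 and 113–168. Their lengths are 9, 19, 28, 28, 28 and 56 days. There is no planned value for this endpoint to reproduce.

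**Identity.** Let D be the days in the interval, made up of Y 'yes' days, N 'no' days and B blank days, so D = Y + N + B. The SAP reports D − Y = N + B. The true number of free days lies between N (all blanks were use days) and N + B (no blank was a use day). The formula always returns the upper limit.

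*Example, one subject, 28 days:* 16 'yes', 4 'no', 8 blank. The SAP result is 28 − 16 = 12. Recorded 'no' days number 4. Scaling the answered-day rate gives 4/20 × 28 = 5.6. The true value is somewhere from 4 to 12. A subject with no entries at all would score 28 − 0 = 28.

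**Expected error.** Let u be the share of days with use and c the share of days with an entry. The documents give neither, so the values below are assumptions. If blanks are unrelated to use:

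- reported = D − D·u·c
- true = D·(1 − u)
- error = D·u·(1 − c)

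For D = 28:

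| u | true free days | error at c = 90% | error at c = 80% |
|---|---|---|---|
| 1.0 | 0 | 2.8 | 5.6 |
| 0.8 | 5.6 | 2.2 | 4.5 |
| 0.5 | 14.0 | 1.4 | 2.8 |

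If blanks are related to use, the error can range from 0 (all blanks on non-use days) to D·(1 − c) (all blanks on use days). At c = 80% the upper end is 28 × 0.2 = 5.6 days.

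**Trend across 28-day intervals.**

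- *False rise.* Use stays at u = 1, so the true value is 0 throughout. If completion falls from 95% to 90% to 80%, the reported values are 28 × 0.05 = 1.4, 28 × 0.10 = 2.8 and 28 × 0.20 = 5.6.
- *Understated rise.* Use falls from u = 1 to u = 0.5, a true rise of 14.0 days. At a stable c = 90% the report goes from 2.8 to 15.4, a rise of 12.6. At a stable c = 80% it goes from 5.6 to 16.8, a rise of 11.2. With constant c the reported rise is c times the true rise.

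**Check on the obvious alternative.** Counting only 'no' days is too low by D·(1 − u)·(1 − c). At u = 0.5, c = 80% this is 2.8 days, since 'no' days average 28 × 0.5 × 0.8 = 11.2 against a true 14.0. The percentage of answered days that are free is 11.2/22.4 = 50%, which is correct when blanks are unrelated to use.

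**Search for an overriding rule.** Protocol 8.1.7 does not address blank days. Protocol 9.3 and SAP 6.3 give general LOCF and non-responder rules, which SAP 8.7 sets aside for this endpoint. SAP 6.6 assigns days to intervals and says nothing about entries or about subjects who have left.

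**The case against.** The strongest counter-argument is textual. No sentence says that a blank is free, the days in the interval are not expressly defined, and the statement that nothing is imputed could be taken to confine the calculation to days with an entry. On that reading the bias disappears. It is the less natural reading: the definition of use and the subtraction are explicit, and SAP 8.7 points to the fixed SAP 6.6 windows. A programmer following the text would count blanks as free.

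Several narrower points stand:

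- The SAP is silent, not wrong, about days after discontinuation or after rollover at Week 16. Taken literally, a rollover subject with no entries in Days 113–168 would score 56 of 56, but a programmer might well exclude that subject.
- The size is unknown. If subjects mostly skip the diary on days when they applied nothing, the error is close to zero. The u = 1 rows assume daily use, whereas the protocol plans tapering.
- Raw counts are comparable only across the three 28-day intervals, so the trend argument applies there.
- The 4-score minimum in SAP 8.5 and 8.6 governs weekly averages. Its absence for a count is not an inconsistency in itself, though it shows that missing entries were foreseen.
- No test or planned decision rests on this endpoint. Table 14.2.2.4.1 is not marked for the interim analysis or the IDMC, and Listing 16.2.6.8 gives the daily data.

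These points limit the consequence. They do not remove the error in the stated formula.

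**Conclusion.** The concern holds and should be fixed. As written, SAP 8.7 reports the highest count of free days that the diary allows, and that count is too high whenever medication was used on any blank day. The direction follows from the formula and needs no assumption about why entries are missing. The illustrated size, about 1.4 to 5.6 days per 28-day interval at 80–90% completion, assumes use on 50–100% of days and missingness unrelated to use. Neither rate is given in the documents. The effect is confined to one descriptive secondary endpoint in a single-group study, and PK, safety and the interim decision are untouched.

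**What to change.** Amend SAP 8.7 as follows:

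1. Count a day as medication-free only when 'no' is recorded, and treat a day without an entry as missing.
2. State that the interval covers only days on which the subject is in the study, so that discontinuation and rollover truncate it.
3. Keep the count, since the protocol names it, and show beside it the number of days answered and the percentage of answered days that are free. The percentage is needed because the 'no' count alone is biased downward. With days answered shown, a reader can also form the limits N and N + B.
4. Optionally, set a minimum completion level for an interval to contribute, in the spirit of the 4-of-7 rule in SAP 8.5 and 8.6.

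The percentage is still biased if skipping the diary depends on use, so the limits in item 3 remain useful.

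The cost is an edit to one SAP section and one or two extra rows in Table 14.2.2.4.1. All the data are already collected. If a minimum is set, fewer subjects contribute to intervals with poor completion.

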8.8. Dermatology Life Quality Index

Dermatology Life Quality Index (DLQI) is a validated 10-item questionnaire for subjects aged > 16 years, covering domains including symptoms/feelings, daily activities, leisure, work/school, personal relationships and treatment. DLQI data will be recorded in the CRF. Children's DLQI (cDLQI) is a

comparable validated 10-item questionnaire designed for pediatric subjects and cDLQI will be used if the subjects are aged 16 years or less. Each question in DLQI/cDLQI has values in a range between 0 (not at all) and 3 (very much) as defined in Table 4:

Table 4: DLQI and cDLQI question point score

Score	DLQI	cDLQI
0	Not at all	Not at all
1	A little	Only a little
2	A lot	Quite a lot
3	Very much	Very much

The DLQI/cDLQI total score is calculated by summing the score of each question resulting in a maximum score of 30 and a minimum of 0. The higher the score, the more quality of life is impaired.

DLQI and cDLQI scores and their change from baseline will be summarized descriptively by visit as continuous variables.

All DLQI/cDLQI data will be listed.

No LOCF analysis will be performed for DLQI/cDLQI.

9. Pharmacokinetics/Pharmacodynamics

PK analyses will be performed using the PK Population. No missing data imputation will be performed.

The serum concentration of nemolizumab will be assessed at baseline, Weeks 1-2, 4, 8, 12, 16, 24 and at any unscheduled visit for safety reasons. At the study drug injection visits (baseline, Weeks 4, 8 and 12), PK samples will be collected within 30 minutes before study drug injection (pre-dose samples). At Weeks 1-2, 16 and 24, attempts should be made to collect PK samples at approximately the same time of the day, to the extent possible.

9.1. Pharmacokinetic Concentration Presentation

Serum concentration data (unit: ng/mL) will be summarized by visit from baseline to Week 24 using the following statistics: n, arithmetic mean, standard deviation, %CV, geometric mean, %CV geometric mean, median, minimum, maximum, 95% CI of mean and number of BLQs (Below Limit of Quantification). BLQ will be considered as missing and excluded from the descriptive summary.

Individual serum concentration and mean concentration will be plotted by visit on both a linear and semi-logarithmic scale on the PK population (unit for x axis: week). For individual concentration plot, BLQ will be considered as missing. For mean concentration plot, mean concentration not calculated will be considered as missing. In addition, individual serum concentration will be plotted over time with different color for subjects with treatment related ADA+ (ADA- at baseline & ADA + after treatment), ADA + at baseline and ADA- from baseline during the study.

Individual serum concentrations will be listed and BLQ will be listed as BLQ.

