# 6.2 Primary Endpoints

#### 6.2.1 Pharmacokinetics

- Nemolizumab serum concentrations at baseline, Weeks 1-2, 4, 8, 12, 16, 24 and unscheduled visits for safety reasons
- Nemolizumab serum PK parameters at steady state extrapolated with a population PK analysis (Cl/F, Vd/F, Tlag, ka, Cmax, Tmax, Ctrough, AUC0-4w, AUC0-8w, AUC0-12w, AUC0-16w, and t1/2)

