#### Notes:

- a Subjects are required to fast for at least 8 hours before the visit(s).
- b Visit 3 is a single visit occurring between Week 1 to Week 2.
- c For subjects that complete the Week 16 visit and will rollover to the nemolizumab LTE study, the Week 16 visit (Visit 7) will serve as the final study visit. See Section 7.6.1.
- A follow-up visit is required for subjects who discontinue after the Week 16 visit and will not rollover to the nemolizumab LTE study. The follow-up visit should occur 12 weeks after the last study drug injection. See Section 7.6.1.
- e Assessments to be conducted at the unscheduled visit(s) depend on the reason for the visit. See Section 7.6.2.
- Subjects who discontinue before the Week 16 visit should attend an early termination visit and a follow-up/final study visit 12 weeks after the last study drug injection. See Section 7.6.1.

CONFIDENTIAL Page 37 of 99

Galderma Research & Development, LLC Protocol Number: RD.06.SPR.116912 21-JUL-2020 Version 6.0

- g Patient-reported efficacy measurements (ACT and DLQI/cDLQI) should occur before investigator (efficacy and safety) assessments, blood sample collections, and study drug administration.
- h Peak and average pruritus NRS should be recorded by subjects once daily in the evening, beginning ≥ 2 weeks before Day 1.
- Sleep disturbance NRS should be recorded by subjects once daily in the morning, beginning ≥ 2 weeks before Day 1.
- Subjects will be asked to record the response (yes/no) to the following question each evening, "Did you apply the eczema medication your doctor gave you, to your skin today?", beginning ≥ 2 weeks before Day 1. See Section 7.5.8.1.1.
- Subjects with a history of asthma will complete the ACT at each study visit before physical examination and other investigator assessments. Subjects with de novo diagnosed asthma will complete the ACT beginning at the first visit of de novo diagnosis and at all follow-up study visits.
- Subjects aged 17 years or older will complete the DLQI, while subjects aged 12-16 years old will complete the cDLQI.

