The duration of the follow-up period (ie, 12 weeks after the last study drug administration), corresponds to 5 half-lives of nemolizumab: the drug plasma level is expected to be lower than the Limit of Quantification at the end of the study, and the follow-up period is therefore considered adequate to ensure the safety of subjects.

Background therapy including moisturizer and authorized TCS will be used throughout this study. This is in line with the current practice to use topical agents in conjunction with systemic treatment in more severe cases. Background TCS will be started from the screening visit, to ensure disease stability and avoid flares. The potency of TCS selected for this study is clinically justified. A medium potency TCS will be used on the body where considered safe (eg, trunk and extremities), and a low potency TCS will be used in TCS-sensitive areas (eg, face, neck, intertriginous areas). The prescribed background TCS use should be within daily frequency limits according to the product labeling. Background TCS use includes guidelines to adjust usage to disease activity and

CONFIDENTIAL Page 39 of 99

tolerability of the subject, including tapering when signs and symptoms improve, discontinuation when lesions clear, and restarting if signs and symptoms recur.

Rescue therapy including topical and systemic treatment or phototherapy may be provided if judged to be necessary by the investigator.

This study will assess the PK and safety profile of nemolizumab in the adolescent population, in order to allow their subsequent enrolment in planned Phase 3 studies.

Nemolizumab serum concentration will be assessed at baseline, Weeks 1-2, 4, 8, 12, 16 and Week 24 and at any unscheduled visit for safety reasons. Given that the nemolizumab drug supply configuration and preparation are similar to that used in the Phase 2b study involving adult AD subjects, no change is anticipated in the absorption phase (ka). Thus, limited PK assessment will be done during the absorption phase and serial pre-dose PK samples will be collected at steady state.

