# 9.4.2 PK Parameters and ADA Analyses

The PK parameters obtained using modelling techniques will be regarded as primary endpoints for the PK analyses (see details in Section 6.4.1). Primary inference for all the PK parameters will be based on the pharmacokinetic analysis population.

The PKPD relationship between nemolizumab plasma concentrations and the selected clinical outcomes (EASI, IGA and NRS) will be investigated, as appropriate, using a PKPD model development based on previous clinical data.

The pop-PK and PKPD models will be detailed in a separate Modeling Analysis Plan.

The concentration at each time point will be summarized as arithmetic mean, standard deviation, median, minimum, and maximum, number of BLQs (Below the Limit of Quantification).

Descriptive statistics (n, arithmetic mean, standard deviation [SD], minimum, median, maximum) will be calculated for all PK parameters obtained using NCA.

For ADA analyses, the incidence of positive ADA results will be summarized (absolute occurrence, percent of subjects, treatment-related ADA). A presentation of ADA results will be detailed in the SAP.

CONFIDENTIAL Page 74 of 99

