3.3. Brief Description

[figure not shown]
This is an open-label, single-group study to evaluate the PK and safety of 30 mg of nemolizumab in adolescent subjects (12 to 17 years of age), with moderate-to-severe AD and associated pruritus. Approximately 20 eligible subjects will be enrolled to receive subcutaneous injections of nemolizumab (30 mg) every 4 weeks over a 16-week treatment period, with a loading dose of 60 mg on Day 1.

Study participation may include a total of 28 weeks for subjects that complete the screening, treatment and follow-up periods. This study includes a 2 to 4-week run-in period followed by a 16-week treatment period. A follow-up visit (Week 24) is scheduled for subjects who will not immediately rollover (within 7 days following the Week 16 visit) into the nemolizumab open-label extension study. Subjects who prematurely discontinue the study before the Week 16 visit have to be followed for 12 weeks after their last dose of study drug.

Subjects will be screened and complete a run-in period of at least 14 days prior to the Baseline visit. Starting on Baseline/Day 1, all eligible subjects will receive nemolizumab administered subcutaneously, in the presence of background TCS therapy. A loading dose of nemolizumab (60 mg) is administered on Day 1, with subsequent nemolizumab dosing of 30 mg occurring every 4 weeks. The final dose of study medication will occur at Week 12 and subjects will complete the treatment period at the Week 16 visit. An 8-week follow-up period is scheduled (Week 24 visit) for subjects who do not immediately rollover (within 7 days following the Week 16 visit) into the nemolizumab open-label extension study. Subjects who prematurely discontinue the study prior to the Week 16 visit have to be followed for 12 weeks after their last dose of study medication.

Assessments of PK, safety, and efficacy will be conducted throughout the study. Subject-reported assessments of pruritus, sleep disturbance and use of topical medication for their eczema will be collected daily.

Figure 1 below shows a description of the Study Design:

: Nemolizumab administration

* : Loading dose (60 mg) at baseline

Abbreviations: BL = Baseline; n = number of subjects; q4w = every 4 weeks; TCS = topical corticosteroid; W =week.

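### SAP 9.1 drops below-quantification results as if missing, so a Week 24 summary that mixes them with quantifiable values overstates residual drug

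*SAP*

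**What the plan says.** SAP 9.1 gives, for each visit from baseline to Week 24, the n, arithmetic and geometric mean, SD, CVs, median, range, 95% CI of the mean and number of BLQs. It then says that "BLQ will be considered as missing and excluded from the descriptive summary". For the figures it adds: "For individual concentration plot, BLQ will be considered as missing". The results stay visible elsewhere: "Individual serum concentrations will be listed and BLQ will be listed as BLQ".

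Protocol 7.3.1 sets follow-up at 12 weeks after the last dose, described as five half-lives, and says that "the drug plasma level is expected to be lower than the Limit of Quantification at the end of the study". The Week 24 concentration belongs to a listed primary PK endpoint in Protocol 6.2.1: "Nemolizumab serum concentrations at baseline, Weeks 1-2, 4, 8, 12, 16, 24 and unscheduled visits for safety reasons". Protocol 9.4.2 asks for the mean, SD, median, range and BLQ count at each time point and does not say to exclude BLQ values.

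Not everyone reaches Week 24. For subjects who move to the extension study, "the Week 16 visit (Visit 7) will serve as the final study visit" (Protocol 7.2, note c). SAP 3.3 likewise schedules the follow-up visit only for those who do not roll over immediately.

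**The concern.** A BLQ sample was drawn and assayed, and the assay showed that the concentration is low. Discarding it as missing removes results because they are low. The rule bites at the one post-dose visit where the protocol itself predicts BLQ results. The Week 24 row should show how much drug remains when safety follow-up ends. As planned, its location statistics can only show values at or above the limit, so the row cannot display the outcome that Protocol 7.3.1 expects.

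The individual plots have a related weakness. A subject who is BLQ at Week 24 has a profile ending at Week 16, and so does a rollover subject who was never sampled at Week 24. On the figure alone, drug washed out and sample not taken look the same.

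**Working it through.** The documents state no figure to reproduce for this point. The check has four steps.

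**1. Which visit is affected?** Inputs from Protocol 7.3.1: 12 weeks = 84 days = 5 half-lives.
- Implied half-life: 84 / 5 = 16.8 days.
- Fraction left after 5 half-lives: 2^-5 = 3.1%.
- Week 16 to Week 24 is 56 days, or 56 / 16.8 = 3.33 half-lives, leaving 2^-3.33 = 9.9% of the Week 16 level under first-order decline.

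A one-compartment simulation used this half-life, an assumed 30% CV on the elimination rate and a log-scale SD of 0.2 on volume. With the limit (LLOQ) assumed at 5, 10 or 15% of the median Week 16 trough, 29, 50 or 64% of Week 24 values are BLQ, against at most 0.2% at Week 16. After dosing, the problem is concentrated at Week 24.

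**2. Direction.** Every value that enters the row is at or above the LLOQ, so the mean, geometric mean, median and minimum are too. Removing the lowest values raises the mean, geometric mean and minimum and cannot lower the median. This holds for any distribution when a visit has at least one BLQ and one quantifiable sample. If all samples are BLQ, nothing is printed.

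**3. Size, under stated assumptions.** Let Week 24 values be lognormal with coefficient of variation CV, and let a share p be BLQ. Write s = sqrt(ln(1 + CV²)), a = Φ⁻¹(p), and φ for the standard normal density. The ratios of the BLQ-excluded statistic to the all-subject value are:
- mean: [1 − Φ(a − s)] / (1 − p)
- median: exp{s · Φ⁻¹((1 + p)/2)}
- geometric mean: exp{s · φ(a)/(1 − p)}

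The CV range is an assumption. The top, 118%, is the Week 24 CV implied by the simulation in step 1; the bottom, 30%, is deliberately favourable to the plan.

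Worked cells at p = 0.5, so a = 0:
- CV 30%: s = 0.294. Mean 0.6155/0.5 = 1.23; median exp(0.294 × 0.674) = 1.22; geometric mean exp(0.294 × 0.798) = 1.26.
- CV 118%: s = 0.934. Mean 0.8248/0.5 = 1.65; median exp(0.934 × 0.674) = 1.88; geometric mean exp(0.934 × 0.798) = 2.11.

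| BLQ share | Mean | Median | Geometric mean |
|---|---|---|---|
| 25% | 1.11–1.26 | 1.10–1.35 | 1.13–1.49 |
| 50% | 1.23–1.65 | 1.22–1.88 | 1.26–2.11 |
| 75% | 1.41–2.41 | 1.40–2.93 | 1.45–3.28 |

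The simulation, which does not assume lognormal Week 24 values, agrees in scale. At 50% BLQ, with a 20% or 30% CV on elimination rate, it gives ratios of 1.57 or 1.73 for the mean, 1.70 or 2.13 for the median and 1.94 or 2.66 for the geometric mean.

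**4. What the rule does not reach.** The two sentences govern the concentration table and plots. SAP 9.2 leaves the calculation of population-PK and NCA parameters to a separate modelling plan, and the NCA areas stop at Week 16.

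**The case against.** The strongest reply is that the effect is disclosed. The table prints n beside the number of BLQs, and every BLQ is listed, so a careful reader can see that the Week 24 statistics rest on quantifiable samples. The row is descriptive and no decision depends on it. This stands, and it is why the point is minor. A count beside a high mean does not correct the mean, however, and nothing labels the statistics as conditional.

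A second reply is that if the protocol's expectation is fully met, all Week 24 samples are BLQ, no mean is printed and nothing is biased. That is right for the all-BLQ case. The bias needs a mixture, and the documents do not allow its likelihood or size to be fixed.

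Three stronger readings are tempting and not supported:
- A reader might infer that the primary PK results are biased. Protocol 9.4.2 says "The PK parameters obtained using modelling techniques will be regarded as primary endpoints for the PK analyses", and BLQ handling for those and for NCA sits in a plan that is not among these documents. They show neither harm nor safety there.
- A reader might infer that the interim comparison with adults is compromised. It is triggered by Week 8 data, and step 1 gives almost no BLQ even at Week 16, four weeks after a dose.
- A reader might infer that washed-out and rollover subjects cannot be separated at all. That is true only of the plot viewed alone; the concentration, visit-date and completion listings separate them.

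**Conclusion.** The point holds and is minor. As written, SAP 9.1 treats an observed low result as missing, and nothing elsewhere in either document reverses it. The upward direction at Week 24 is certain whenever BLQ and quantifiable samples are mixed. The size is illustrative: about 1.1 to 1.3 times for the mean at 25% BLQ and 1.2 to 1.7 times at 50%, given lognormal values and an assumed CV of 30% to 118%. The LLOQ, the Week 24 variability and the number attending are not stated, so no single figure can be defended. The finding is confined to the descriptive concentration table and the individual plots.

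**What to change.** Replace the two BLQ sentences in SAP 9.1 with:

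> BLQ results are observed values below the LLOQ, not missing data. At each visit, report the number sampled and n (%) BLQ. The median and minimum use all sampled subjects with BLQ ranked lowest, and are shown as BLQ where applicable. If more than 50% of results at a visit are BLQ, the mean, SD, %CV, geometric mean, geometric %CV and CI are not shown. Otherwise, when any BLQ is present, these statistics are all computed on quantifiable samples and labelled as such. On individual plots, post-dose BLQ is drawn at the LLOQ with a distinct symbol.

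No value is substituted, so the rule against imputing PK data in Protocol 9.3 and SAP 9 is kept. Using LLOQ/2 in the arithmetic mean alone is not advised. It sits awkwardly with that rule, and at 50% BLQ the quantifiable-only geometric mean would print 38% to 44% above the arithmetic mean in the same row (CV 30% to 118%).

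SAP 14 currently foresees no changes from the protocol. It should declare that means and SDs are withheld above 50% BLQ, because Protocol 9.4.2 asks for them at each time point.

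The cost is one paragraph in SAP 9.1, one line in SAP 14, and edits to Table 14.2.3.1 and the concentration figures (14.2.3.5 to 14.2.3.7). No new data are needed. There are two downsides. Any mean or geometric mean printed with BLQs present still covers quantifiable samples only, now labelled. Week 24 may also show no mean: if the true BLQ share is 50%, the binomial chance that more than half the samples are BLQ is 50, 38 or 41% with 5, 10 or 20 attending. The median, minimum and n (%) BLQ then carry the all-subject result. The 50% cut-off and the plot symbol are choices the sponsor may adjust.
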